7.2 Sample Size

Assuming disease prevalence at baseline of 99%, if ctDNA is detectable in at least 39 out of 49 patients, this will enable us to demonstrate a sensitivity of at least 70% (i.e. rule out the maximum futility proportion), and assume a true sensitivity of 85% (the minimum efficacy proportion), with 80% power and a one-sided type I error of 0.05.”

If ctDNA is undetectable in at least 112 out of 121 patients, this will enable us to demonstrate a specificity of at least 85% (i.e. rule out the maximum futility proportion), and assume a true specificity of 95% (the minimum efficacy proportion), with 90% power and a one-sided type I error of 0.01 (Single stage phase II A'Hern design, software used nQuery v8.7.2).

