4. TRIAL PROCEDURES

4.1 Patient Identification and Consent

The proposed observational sample collection study will recruit patients referred to the neck lump clinics via the SCR pathway. Patients are classified as low and high risk in the neck lump clinic following clinical history and examination by the clinician. Patients classified as high risk are

referred for an USFNA. These patients will be approached for screening by a designated study research nurse and be provided with a patient information sheet (PIS). They will be made aware that definite eligibility will be determined following USFNA. Patients will only be eligible if they do not have a lump in their thyroid gland after undergoing USFNA. Following USFNA, eligible patients will be approached by the research nurse to address any concerns and to sign an informed consent.

Blood sample will be collected from patients who sign the informed consent. As per the study procedure, the patient will be consented on the same day i.e. the day of the neck lump clinic, that they receive the consent form. They will be given adequate time to consider consenting to the study and have the opportunity to ask questions.

The blood sample will be transferred to the Biobank at RMH via first class post for processing and storage. These samples will then be transferred in batches to ICR or CMP and analysed for the presence of and to quantify the levels of ctDNA. With advances in technologies for analysis we will also perform a complete genomic analysis.

The study will be run at head and neck lump clinics at Kingston Hospital NHS Foundation Trust and London North West University Healthcare NHS Trust.

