7.4 Study duration

The study will continue until up to 49 patients with invasive HNSCC and 121 patients without invasive SCC, have been recruited. The study will be completed once all 170 patients have been recruited and samples analysed.

The study will be run at the head and neck lump clinics at Kingston Hospital NHS Foundation Trust and London North West University Healthcare NHS Trust. Based on previous year's figures, approximately 200 patients are referred each year for USFNA following assessment in the clinic. Of these, 30-40 patients get diagnosed with HNSCC and 10-15 with Thyroid cancer. Therefore, we anticipate that this study will complete recruitment in 9-12 months.

The primary analysis will be performed once all 49 patients with invasive HNSCC are recruited and samples analysed, whereas the secondary endpoint analysis will be performed once 121 patients without invasive HNSCC have their samples analysed.

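### The 49 cases, the total of 170 and the 9-12 months in sections 7.2 and 7.4 cannot all hold at the plan's own rate of 30-40 HNSCC diagnoses a year

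*Combined protocol and SAP*

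**What the plan says.** Section 7.2 bases sensitivity on 49 patients ("Assuming disease prevalence at baseline of 99%, if ctDNA is detectable in at least 39 out of 49 patients"), with a null of 70%, an alternative of 85% and error rates stated as "with 80% power and a one-sided type I error of 0.05". Specificity has its own group: "If ctDNA is undetectable in at least 112 out of 121 patients, this will enable us to demonstrate a specificity of at least 85"%. Section 7.1 describes the two groups as 49 patients with HNSCC and 121 without.

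Section 7.4 gives two recruitment rules. Recruitment runs until up to 49 cases and 121 non-cases are in, and the primary analysis waits for all 49 cases. It also says: "The study will be completed once all 170 patients have been recruited and samples analysed". Recruitment is expected to take 9-12 months, from about 200 USFNA referrals a year: "Of these, 30-40 patients get diagnosed with HNSCC and 10-15 with Thyroid cancer".

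Sections 3.3 and 4.1 admit patients referred for USFNA who turn out to have no thyroid lump. Consent is taken on the day of the clinic: "Following USFNA, eligible patients will be approached by the research nurse to address any concerns and to sign an informed consent". No criterion refers to HNSCC status, and no rule limits how many non-cases are enrolled.

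**The concern.** The groups of 49 and 121 are defined by a diagnosis that eligibility does not use. The number of cases among those enrolled is therefore set by the case mix of the clinic. A 49:121 split needs 49/170 = 28.8% of enrolled patients to have HNSCC, while section 7.4 reports 30-40 in about 200 referrals, or 15-20% before exclusions.

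Sensitivity is the primary endpoint, and section 7.1 makes a value above 70% the condition for a larger study. If recruitment closes at 170 with too few cases, that decision rests on an underpowered test. If recruitment runs on to 49 cases, the stated duration is wrong, the stated total is very probably wrong, and the plan does not say which 121 of the surplus non-cases the specificity rule uses.

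**Working it through.** **Inputs.** Section 7.2: 70% v 85%, one-sided 0.05, power 0.80; 85% v 95%, one-sided 0.01, power 0.90. Section 7.4: about 200 referrals, 30-40 HNSCC and 10-15 thyroid cancers a year; 170 patients; 9-12 months.

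**1. The plan's sizes.** An exact single-stage binomial search gives the smallest n as 49 for sensitivity (cut-off 40, alpha 0.048, power 0.809) and 121 for specificity (cut-off 112, alpha 0.0093, power 0.918). Both sizes reproduce, and neither uses a prevalence. (The printed cut-off of 39 out of 49 has exact alpha 0.092. That is a separate matter and does not affect what follows.)

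**2. Cases in the stated time.** Cases = yearly HNSCC × months/12, with every patient consenting.
- 9 months: 30 × 9/12 = 22.5 to 40 × 9/12 = 30.
- 12 months: 30 to 40.
- Months to 49 cases: 49/40 × 12 = 14.7 to 49/30 × 12 = 19.6.

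This step needs no assumption about thyroid lumps. The stated 9-12 months fits other targets: 170 patients of any mix take 170/190 × 12 = 10.7 to 170/185 × 12 = 11.0 months, and 121 non-cases take 9.1-10.0 months, by which time about 23-33 cases would have accrued.

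**3. Cases in 170, removing thyroid cancers only.** Share = HNSCC/(200 − thyroid cancers).

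| HNSCC | Thyroid cancers | Share | Cases in 170 | Enrolled for 49 cases | Of whom non-cases |
|---|---|---|---|---|---|
| 30 | 10 | 15.8% | 26.8 | 310 | 261 |
| 30 | 15 | 16.2% | 27.6 | 302 | 253 |
| 40 | 10 | 21.1% | 35.8 | 233 | 184 |
| 40 | 15 | 21.6% | 36.8 | 227 | 178 |

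At these shares the binomial probability of at least 49 cases in 170 is 0.00001 to 0.017.

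**4. Allowing for benign thyroid lumps.** The exclusion covers any thyroid lump, and the plan counts only cancers. The number of lumps is an assumption; 30-60 per 200 is used to show the range.
- Cases in 170: 170 × 30/170 = 30 to 170 × 40/140 = 48.6.
- Enrolled for 49 cases: 49 × 140/40 = 172 to 49 × 170/30 = 278.
- Lumps needed for 170 to hold 49 cases on average: 200 − 40 × 170/49 = 61 to 200 − 30 × 170/49 = 96.

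**5. Power if recruitment closes at 170 regardless of mix.** Exact test of 70% at one-sided 0.05, true sensitivity 85%.
- 27 cases: cut-off 24, power 0.41.
- 32 cases: cut-off 28, power 0.46.
- 37 cases: cut-off 31, power 0.68.

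Power does not rise steadily with the number of cases, because the cut-off moves in whole patients. It stays within 0.41-0.68 for every number of cases from 27 to 37.

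**The case against.** The strongest reply is that section 7.4 sets quotas. It recruits to 49 and 121 and ties the primary analysis to the 49th case, so the 170 in the completion sentence may simply be their sum. On that reading the 80% power is kept. This stands: a reader might infer that the power is certainly lost, and the documents do not support that. The quota reading does not reconcile the figures, however. 49 cases still take about 15-20 months, and with same-day consent and no criterion on HNSCC status they need more than 170 enrolled unless at least 61-96 of 200 referrals are thyroid lumps.

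A second reply is that 16-22% is not a figure the plan gives. This also stands. It is a lower range, and at an assumed 60 lumps with 40 HNSCC a year, 170 patients would hold nearly 49 cases. The duration conflict does not depend on it.

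It is also tempting to call the 99% prevalence the source of the error, or wrong however it is read. The documents do not support that. The calculation does not use it, and it may loosely mean that nearly all of the 49 have disease.

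Nor does a surplus of non-cases by itself break the specificity rule, because section 7.4 triggers that analysis at 121. What is missing is which 121. Finally, that diagnosis comes after consent is inferred from same-day consent and the tissue reference standard; the documents give no date for the result.

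**Conclusion.** The point holds as a conflict among the plan's own figures. At 30-40 cases a year, 49 cases cannot be reached in 9-12 months even if every patient consents. This is the firmest part. That 170 enrolled patients will fall short of 49 cases is very likely on the plan's figures (about 27-37 cases if only thyroid cancers are removed), but its size depends on the unreported number of benign thyroid lumps (about 30-49 cases at an assumed 30-60 per 200).

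The consequence depends on which sentence of section 7.4 governs. A stop at 170 with 27-37 cases leaves power of about 0.41-0.68 against the stated 0.80. Recruitment to 49 cases preserves the power and makes the 9-12 months wrong, and the 170 too unless thyroid lumps are very common. Less than full consent would lengthen recruitment further. These are figures that a sponsor and sites rely on, and the text should be corrected before recruitment is planned around them.

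**What to change.** In section 7.4:
- State that 49 and 121 are the numbers in the accuracy analyses and that 170 is not the recruitment total.
- Recruit consecutive eligible patients, whatever the suspected diagnosis, until the 49th confirmed HNSCC. This avoids enriching late recruitment with patients who look like cancer, which would change the group that the sensitivity describes.
- Restate expected enrolment as about 230-310 if only thyroid cancers are excluded, and fewer if benign thyroid lumps are common. Give the assumed number of lumps.
- Restate the duration as about 15-20 months or longer.
- Apply the 112 out of 121 rule to the first 121 consecutive non-cases by sample date, and bank or describe the rest.

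If the sponsor will not go beyond 170, state the expected cases and power for that total, with the thyroid-lump assumption shown.

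In section 7.2, as a side point, delete the 99% prevalence. It cannot describe the recruited population, and removing it changes neither sample size.

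The cost is more than wording. It is a longer stated recruitment period with consent, collection and banking for the extra patients (about 60-140 beyond 170 if only thyroid cancers are excluded: 230 − 170 to 310 − 170), or a less favourable stated power. Surplus non-case samples need not be sequenced for the accuracy analyses.

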7. STATISTICS AND DATA ANALYSIS

7.1 Statistical Considerations

This is a pilot study that aims to investigate the feasibility of using HPV DNA as a biomarker of early diagnosis of HNSCC. To this effect, we will focus on identifying the sensitivity of the NGS assay in patients who been diagnosed with invasive cancer. A sensitivity of greater than 70% would be necessary for further investigation in a larger study. We hope to recruit 49 patients who undergo USFNA and are diagnosed with HNSCC and a further 121 patients who undergo USFNA and do not have invasive HNSCC. The standard ctDNA test will be compared against the tissue diagnosis of invasive cancer as per the tumour biopsy.

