7.3 Statistical analysis

The statistical analyses will be performed by [name] [name], who is a co-investigator on the project using the R statistical software package. Given, that the study will involve simple statistical analyses, an expert statistician will not be required to perform the analyses. However, we will ask the study statistician to check the analyses for accuracy.

All quantitative data will be analysed for normality and presented accordingly as number of observations, measure of central tendency for HPV DNA copy number and variance. Qualitative data will be presented as a number of observations and percentages

A Chi square test will also be performed to check for the association between plasma ctDNA and the diagnosis of viable invasive HNSCC.

Sensitivity at baseline is defined as the proportion of participants with invasive HNSCC who have ctDNA detected.

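### The primary success rule of at least 39/49 has an exact one-sided type I error of 0.092, not 0.05; the stated inputs give a threshold of 40/49

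*Combined protocol and SAP*

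**What the plan says.** Section 7.2 (Sample Size) gives the rule for the primary endpoint: "if ctDNA is detectable in at least 39 out of 49 patients, this will enable us to demonstrate a sensitivity of at least 70"%. It treats 70% as the proportion to be excluded and continues "assume a true sensitivity of 85% (the minimum efficacy proportion"). The operating characteristics follow: "with 80% power and a one-sided type I error of 0.05". The section closes with the design and software, "Single stage phase II A'Hern design, software used nQuery v8.7.2", printed after the specificity rule. That rule requires at least 112 undetectable results in 121 patients, with 85% against 95%, 90% power and a one-sided error of 0.01.

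Section 7.1 makes the comparison with 70% the condition for going further: "A sensitivity of greater than 70% would be necessary for further investigation in a larger study".

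Section 7.3 defines sensitivity as the proportion of participants with invasive HNSCC in whom ctDNA is detected. It gives no test or confidence interval for that proportion against 70%. The one test it names is for association: "A Chi square test will also be performed to check for the association between plasma ctDNA and the diagnosis of viable invasive HNSCC".

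**The concern.** A threshold of 39 in 49 is an observed sensitivity of 39/49 = 79.6%. In a sample of 49 that looked too low to exclude 70% at a one-sided 0.05 level by an exact method. If so, the count and the error rate printed beside it cannot both be right.

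This is the only numerical rule for the primary endpoint, and it decides whether the assay goes forward to a larger study. If the threshold is one too low, an assay with a true sensitivity of only 70% passes more often than the plan says, and a result of 39/49 would be reported as excluding 70% when it does not. Nothing later in the plan would catch this. Section 7.3 has no test against 70%, and the statistician's check described there covers the analyses, not the planned threshold.

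**Working it through.** **Inputs, all from section 7.2:** n = 49; threshold r = 39, with success meaning r or more; p0 = 0.70; p1 = 0.85; one-sided type I error 0.05; power 0.80.

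**1. Does n = 49 reproduce?** Yes. The normal approximation gives

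n = [(1.645 × √(0.70 × 0.30) + 0.842 × √(0.85 × 0.15)) / 0.15]² = 49.4.

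An exact search takes the smallest n for which the smallest r with P(X ≥ r | p0) ≤ 0.05 also has P(X ≥ r | p1) ≥ 0.80. It returns n = 49 with r = 40. The plan's sample size is confirmed; its threshold is not.

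**2. Properties of each threshold.** With X ~ Binomial(49, p), the type I error is P(X ≥ r | 0.70) and the power is P(X ≥ r | 0.85):

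| Success if at least | Type I error | Power |
|---|---|---|
| 38/49 | 0.159 | 0.945 |
| 39/49 (as printed) | 0.0921 | 0.893 |
| 40/49 | 0.0480 | 0.809 |
| 41/49 | 0.0222 | 0.690 |

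Only 40 meets both stated figures. The type I error of the printed rule is 0.0921/0.05 = 1.84 times the stated level.

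**3. Control on the specificity rule.** The same search with p0 = 0.85, p1 = 0.95, error 0.01 and power 0.90 returns n = 121 with r = 112 (type I error 0.0093, power 0.918), exactly as printed. This supports both the method and the literal reading of the words at least.

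**4. Confidence bound at the threshold.** The exact (Clopper-Pearson) one-sided 95% lower bound for x of n is the 5th percentile of Beta(x, n − x + 1):

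- 39/49: Beta(39, 11) gives 0.678, so 70% is not excluded.
- 40/49: Beta(40, 10) gives 0.701, so 70% is excluded.

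**5. Could another method or reading give 39?**

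- Normal test: z = (39 − 34.3)/√(49 × 0.21) = 1.465, p = 0.071. With continuity correction, p = 0.095.
- Mid-p: 0.0480 + ½ × (0.0921 − 0.0480) = 0.070.
- 99% prevalence read as 48 true cases (49 × 0.99 = 48.5): at least 39/48 has type I error 0.057 and power 0.826.
- 99% prevalence read as both detection rates multiplied by 0.99: type I error 0.076.
- Other one-sided 95% lower bounds at 39/49: Wilson 68.7%, Jeffreys 69.0%, Agresti-Coull 68.6%, Wald 70.1%.

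None of the tests reaches 0.05. Only the Wald bound passes 70%. The plan does not name it, and using it would leave the rule's actual error rate at 0.092.

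**The case against.** The design label is printed only after the specificity sentence, so applying it to sensitivity is an inference. That is correct. The inference is strong, because the search reproduces n = 49 exactly, and the error does not depend on the label: 0.092 is the error rate of the printed rule whatever design it is called.

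The prevalence assumption leaves a second reading open, with 48 true cases, under which 39 has a type I error of 0.057, a much smaller excess. But sections 7.1 and 7.4 fix the denominator at 49 patients with HNSCC, and 0.057 is still above 0.05.

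The practical difference is a single outcome. The two rules disagree only at exactly 39 detections, which has probability 0.0921 − 0.0480 = 0.044 at a true sensitivity of 70% and 0.893 − 0.809 = 0.084 at 85%. The study is an observational pilot, and the rule governs progression to a larger study, not anyone's care. All of this is true and limits the consequences. It does not make the stated error rate correct.

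Finally, the plan nowhere says that the chi-square test decides the primary endpoint. That stands too. The absence of a test against 70% in section 7.3 is a related gap, not part of the arithmetic error.

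**Conclusion.** The threshold is wrong as written. At least 39 of 49 has an exact one-sided type I error of 0.092 against the stated 0.05, and a power of 89% against the stated 80%. At least 40 of 49 gives 0.048 and 81%. The sample size of 49 and the specificity rule are both correct.

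These figures assume that the 49 patients with HNSCC are independent and form the denominator, and that 70% and 85% are the null and alternative sensitivities as section 7.2 states. The most likely explanation is that 39 is the largest count that fails and was written down as the smallest that succeeds. The documents do not prove this, and the conclusion does not need it. Because this is the primary go/no-go rule, it should be corrected before results are known.

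**What to change.** In section 7.2, replace 39 by 40 in the sensitivity rule, and report the exact properties: type I error 0.048, power 81%. State that the single-stage exact design applies to both endpoints, and explain the 99% prevalence assumption or remove it.

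In section 7.3, add one sentence: the primary endpoint is met if the exact (Clopper-Pearson) one-sided 95% lower bound for sensitivity exceeds 70%. With 49 evaluable patients this is the same rule as at least 40. It also gives the right cut-off if the number differs. With 48 evaluable patients the threshold stays at 40 (39/48 gives 0.057, 40/48 gives 0.027, with power 71%), and with 50 patients a count of 40 is not enough (0.079). The same sentence can say that the chi-square test is descriptive and does not bear on the primary conclusion.

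The cost is one number and a few sentences. Recruitment is unchanged. Power falls from the 89% of the printed rule to 81%, which is still above the 80% the plan asks for.

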7.3 Statistical analysis

The statistical analyses will be performed by [name] [name], who is a co-investigator on the project using the R statistical software package. Given, that the study will involve simple statistical analyses, an expert statistician will not be required to perform the analyses. However, we will ask the study statistician to check the analyses for accuracy.

All quantitative data will be analysed for normality and presented accordingly as number of observations, measure of central tendency for HPV DNA copy number and variance. Qualitative data will be presented as a number of observations and percentages

A Chi square test will also be performed to check for the association between plasma ctDNA and the diagnosis of viable invasive HNSCC.

Sensitivity at baseline is defined as the proportion of participants with invasive HNSCC who have ctDNA detected.

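### Section 7.3 names no analysis that tests sensitivity against 70% or specificity against 85%, and the 39/49 rule in 7.2 that would fill the gap has a type I error of 0.092, not 0.05

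*Combined protocol and SAP*

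**What the plan says.** All references are to the combined protocol and SAP.

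- **Section 3.2** makes sensitivity the primary and specificity the secondary endpoint.
- **Section 7.1** sets the condition for going on: "A sensitivity of greater than 70% would be necessary for further investigation in a larger study". It does not say whether this means the observed proportion or a confidence bound.
- **Section 7.2** names a single-stage A'Hern design and gives a count rule for each endpoint. For sensitivity: "if ctDNA is detectable in at least 39 out of 49 patients, this will enable us to demonstrate a sensitivity of at least 70" per cent, with an assumed true value of 85%, "with 80% power and a one-sided type I error of 0.05". For specificity: "If ctDNA is undetectable in at least 112 out of 121 patients, this will enable us to demonstrate a specificity of at least 85" per cent, with an assumed true value of 95%, 90% power and a one-sided type I error of 0.01.
- **Section 7.3** plans summaries of quantitative data and, for the rest, "Qualitative data will be presented as a number of observations and percentages". It then adds: "A Chi square test will also be performed to check for the association between plasma ctDNA and the diagnosis of viable invasive HNSCC". It defines sensitivity as a proportion but does not define specificity. It names no confidence interval and no test against 70% or 85%, and it does not refer to the rules in 7.2.
- **Section 7.4** stops recruitment at up to 49 patients with and 121 without invasive disease, and times each endpoint's analysis to its own group.

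**The concern.** The study's question is one-sample: does sensitivity exceed 70%, and does specificity exceed 85%? The only test named in the analysis section is two-sample. Its null hypothesis is that the detection rate is the same in patients with and without HNSCC, that is, sensitivity = 1 − specificity. A small p-value would not bear on either target.

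The targets therefore rest on the count rules in 7.2, which raises two difficulties. The rules are tied to exact denominators, with no instruction if the evaluable number differs. And the sensitivity rule has to be right, because nothing in 7.3 would reveal an error in it. At stake is the decision to fund and run a larger study. Section 7.3 gives the analysis to a co-investigator, with the study statistician checking it afterwards, so the written text has to carry the method.

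**Working it through.** **Inputs.** From 7.2, sensitivity: p0 = 0.70, p1 = 0.85, one-sided α = 0.05, power 0.80, rule ≥ 39 of 49. Specificity: p0 = 0.85, p1 = 0.95, one-sided α = 0.01, power 0.90, rule ≥ 112 of 121. From 7.4: about 200 USFNA referrals a year, 30–40 with HNSCC, 10–15 with thyroid cancer, 170 patients in total.

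**1. Reproducing the design.** The A'Hern design takes the smallest n for which some r satisfies P(X ≥ r | n, p0) ≤ α and P(X ≥ r | n, p1) ≥ power, with X binomial.

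| Endpoint | Smallest n | r | Type I error | Power |
|---|---|---|---|---|
| Sensitivity | 49 | 40 | 0.048 | 0.809 |
| Specificity | 121 | 112 | 0.0093 | 0.918 |

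Both sample sizes reproduce, and so does the specificity count of 112. The sensitivity count does not: the design gives 40, and the document prints 39.

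**2. Size of the discrepancy.** Moving from 40 to 39 adds P(X = 39).

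- At p = 0.70: 0.0480 + 0.0441 = 0.0921.
- At p = 0.85: 0.8089 + 0.0838 = 0.8926 (rounding in the last digit).

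The printed rule therefore has a type I error of 0.092 and power of 0.893.

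**3. The same result as bounds.** The Clopper-Pearson one-sided lower bound is the α quantile of a Beta(x, n − x + 1) distribution.

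| Result | Level | Lower bound | Target excluded? |
|---|---|---|---|
| 39/49 (79.6%) | 95% | 67.8% | 70%: no |
| 40/49 (81.6%) | 95% | 70.1% | 70%: yes |
| 112/121 (92.6%) | 99% | 85.1% | 85%: yes |

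**4. What the chi-square test responds to.** No significance level or continuity correction is stated. I assume two-sided 0.05 and show both forms. The table gives the lowest observed sensitivity that reaches significance.

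| False positives (observed specificity) | With correction | Without |
|---|---|---|
| 6/121 (95.0%) | 8/49 = 16.3%, p = 0.033 | 7/49 = 14.3% |
| 9/121 (92.6%) | 10/49 = 20.4%, p = 0.031 | 9/49 = 18.4% |
| 18/121 (85.1%) | 15/49 = 30.6%, p = 0.033 | 14/49 = 28.6% |

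For example, 8/49 against 6/121 gives 170 × (|8×115 − 41×6| − 85)² / (49 × 121 × 14 × 156) = 4.55. Every threshold in the table is far below 70%.

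**5. Denominators other than 49.** Removing thyroid cancers leaves 200 − 15 = 185 to 200 − 10 = 190 referrals a year. In 170 consecutive patients that implies 170 × 30/190 = 26.8 to 170 × 40/185 = 36.8 cases, about 27 to 37. This assumes equal uptake by diagnosis and treats thyroid cancers as the only thyroid exclusions. The exact rule is the smallest r with P(X ≥ r | n, 0.70) ≤ 0.05. The last two columns show what happens if 39/49 is instead scaled in proportion and rounded up.

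| Cases | Exact rule | Type I error | Power at 85% | Scaled 39/49 | Type I error |
|---|---|---|---|---|---|
| 27 | 24 | 0.020 | 0.41 | 22 | 0.136 |
| 37 | 31 | 0.044 | 0.68 | 30 | 0.095 |
| 40 | 34 | 0.024 | 0.61 | 32 | 0.111 |

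The exact rule holds its error rate at any number. It does not restore the lost power.

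**The case against.** The strongest reply is that the plan already contains the right analysis. An A'Hern design is an exact one-sample binomial test, 7.2 states its outcome as a count for each endpoint, and 7.3 says that the chi-square test is *also* performed. This stands in large part. A reader of 7.3 alone might infer that the chi-square test is the study's only inference, or that the go decision will rest on its p-value. The documents do not support that, and the test need not be removed.

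A reader might also infer from 7.1 that any observed sensitivity above 70% suffices. Under that reading 35/49 would pass, with probability 0.48 at a true 70%. But 7.2 treats 70% as a value to be ruled out and sets the threshold at 39. Taken together, the two sections give a false-go risk of 0.092. What remains is that 7.1 should say what it means.

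Finally, a reader might infer that 49 and 121 cannot be reached. That is not shown. Section 7.4 ties each analysis to its own target, and the yearly figures bear first on duration. They do show that 170 consecutive patients would be unlikely to split 49 to 121, and unusable samples could also change the counts. The plan has no rule for that case.

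The reply does not rescue the sensitivity rule. Following 7.2 as written applies 39/49, which misses its own stated error rate.

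**Conclusion.** The point holds in a limited form. Section 7.3 does not carry the hypotheses of 7.2 into the analysis, and its one named test addresses neither target. The rules in 7.2 cover this only at exactly 49 and 121. At 49, the sensitivity rule has a type I error of 0.092, nearly twice the stated 0.05. The specificity rule is sound.

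The figures for 39/49, 40/49 and 112/121 are exact and rest only on the stated design values. The chi-square thresholds of about 16–20% are illustrations. They depend on an observed specificity of about 93–95%, a continuity correction and an assumed two-sided 0.05, and they rise to about 29–31% at 85% specificity. The conclusion that the test does not address the targets needs none of them. The change should be made before analysis; it does not call the design or the sample sizes into question.

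**What to change.** 1. **Section 7.3:** make the primary analysis of each endpoint an exact one-sided binomial test on the evaluable patients actually obtained. Claim sensitivity if the Clopper-Pearson one-sided 95% lower bound exceeds 70%, and specificity if the one-sided 99% lower bound exceeds 85%. At the planned numbers these rules are 40/49 and 112/121.
2. **Section 7.3:** define specificity alongside sensitivity, and report exact confidence intervals for both. Two-sided 90% (sensitivity) and 98% (specificity) intervals have the decision bound as their lower limit. If 95% intervals are also wanted, say that they are not the decision rule.
3. **Section 7.3:** label the chi-square test as supplementary.
4. **Section 7.2:** change 39 to 40.
5. **Section 7.1:** state that the 70% criterion refers to the lower bound, not the observed proportion.

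The cost is protocol wording and a few lines of R, with no extra patients or samples. The go criterion becomes one case stricter: power at a true 85% falls from 0.89 to 0.81, still above the stated 80%. If fewer than 49 cases are evaluable, the test stays valid but the power falls, and the report should say so.
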